### **18.3 Study Monitoring**

Before study initiation, at a site initiation visit or at an Investigator's meeting, a Eleven Biotherapeutics Inc. representative, or designee, will review the protocol and eCRFs with the Investigators and their study site staff. During the study, a monitor will visit the site regularly to check the completeness of subject records, the accuracy of entries on the eCRFs, the adherence to the protocol and to Good Clinical Practice (GCP), the progress of enrollment, and to ensure that study drug is being stored, dispensed, and accounted for according to specifications. Key study personnel must be available to assist the monitor during these visits.

The Investigator must maintain source documents for each subject in the study, consisting of case and visit notes (hospital or clinic medical records) containing demographic and medical information, contact notes, laboratory data, and the results of any other tests or assessments. All information on

eCRFs must be traceable to these source documents in the subject's file. Data not requiring a separate written record will be defined before study start and will be recorded directly on the eCRFs, which will be documented as being the source data. The Investigator must also keep the original Informed Consent form signed by the subject (a signed copy is given to the subject).

#### **18.4 Audits and Inspections**

Eleven Biotherapeutics Inc. Quality Assurance or their representatives may conduct audits at the study site(s). Audits will include, but are not be limited to: compliance with the protocol, compliance with IRB procedures, audit trail of data handling and processes, Standard Operating Procedures, drug supply, presence of required documents, informed consent process, and comparison of data on eCRFs with source documents. The Investigator agrees to accommodate and participate in audits conducted at a reasonable time and manner, as needed.

Regulatory authorities may also audit the Investigator during or after the study. The Investigator should contact Eleven Biotherapeutics Inc. immediately if this occurs. Additionally, the Investigator must fully cooperate with governmental (e.g., FDA or Health Canada) audits.

### **19 QUALITY CONTROL AND QUALITY ASSURANCE**

All clinical work conducted under this protocol is subject to GCP and ICH guidelines. The study will be subject to inspection by regulatory authorities (e.g., FDA or Health Canada) and Eleven Biotherapeutics Inc. or its representatives, and will be monitored by authorized personnel to ensure adherence to the protocol and these regulations and guidelines. The purpose of these efforts is to ensure that the trial is conducted and data are collected, documented, and reported in compliance with the protocol, GCP, and all applicable regulatory requirements.

The Investigator agrees to give access to all relevant data and records to Eleven Biotherapeutics Inc., clinical Quality Assurance representatives, monitors, and auditors, as well as to Institutional Review Boards/Independent Ethics Committees (IRBs/IECs) and regulatory authorities, as required. If an inspection of the clinical site is requested by a regulatory authority, the Investigator must inform Eleven Biotherapeutics Inc. immediately that this request has been made. It is the responsibility of the Investigator and their relevant personnel to be available during the monitoring visits and possible audits and that sufficient time is devoted to the process.

By signing the Informed Consent form, a study subject authorizes access to his/her confidential medical records by the Sponsor's clinical monitor and/or regulatory authorities for the purpose of comparing these source documents with subject eCRFs, and to verify compliance with the protocol.

### **20 ETHICS**

This clinical study is designed and shall be implemented and reported in conformance with the ICH Harmonized Tripartite Guidelines for Good Clinical Practice, and in accordance with FDA regulations and guidelines and applicable federal, state, and local laws, and with the ethical principles laid down in the Declaration of Helsinki. Prior to study start, the Investigator is required to sign a protocol signature page confirming his/her agreement to conduct the study accordingly.

## **20.1 Independent Ethics Review**

It is the responsibility of the Investigator to obtain approval of the protocol, Informed Consent form, and any other documents or information that are likely to be presented to the subject by a properly constituted IRB/IEC. Copies of IRB/IEC approvals must be forwarded to Eleven Biotherapeutics Inc. before study initiation. The IRB/IEC must agree to review the study progress periodically, at intervals not to exceed 1 year and give yearly written approval to continue the study. A copy of this approval, referring to study title and number, must be forwarded to Eleven Biotherapeutics Inc.

The Investigator must also provide any revisions to the Informed Consent form or protocol amendments to the IRB/IEC for approval, and forward copies of the approval to Eleven Biotherapeutics Inc. Any revisions that may increase subject risk exposure must be approved by the IRB/IEC prior to implementation. Administrative changes (such as changes in address and phone number) must be sent to IRBs/IECs, but do not require approval.

In addition, the Investigator is responsible for reporting any serious or unexpected AEs to the IRB/IEC.

## **20.2 Subject Information and Informed Consent**

It is the responsibility of the Investigator to provide each subject (or the subject's legally authorized representative) full and adequate verbal and written information regarding the objective and procedures of the trial and the possible risks involved before inclusion in the trial.

Eligible subjects may only be included in the study after providing signed, written (witnessed, where required by law or regulation), IRB- or IEC-approved informed consent, or, if incapable of doing so, after such consent has been provided by a legally acceptable representative of the subject. A copy of the Informed Consent form must be given to each subject. Subjects must be informed of their right to withdraw from the trial at any time.

Informed consent must be obtained before conducting any study-specific procedures (i.e., all of the procedures described in the protocol, including Screening procedures). The process of obtaining informed consent should be documented in the subject source documents.

## **21 RETENTION OF RECORDS**

The Investigator agrees to keep study-related records, including identity of all study participants, original signed and dated Informed Consent forms, copies of all CRFs, source documents, and detailed records of drug disposition and all other study-specific documentation in accordance with ICH Guidelines to enable evaluations or audits from regulatory authorities or Eleven Biotherapeutics Inc. or its representatives. ICH requires the following:

Essential documents should be retained until at least 2 years after the last approval of a marketing application in an ICH region and until there are no pending or contemplated marketing applications in an ICH region or at least 2 years have elapsed since the formal discontinuation of clinical development of the investigational product.

## 22 PUBLICATION POLICY

All information obtained during the conduct of this study will be regarded as confidential, and written consent from the Sponsor is required prior to disclosing any information relative to this study. Copies of any publication, written presentation of data, or script of an oral presentation of the data must be provided to the Sponsor at least 30 days prior to submission for publication or presentation. This requirement is to assure concurrence regarding data, evaluations, and conclusions, as well as to communicate any new or unpublished information that may be relevant, and to protect the Sponsor's intellectual property.

Nothing in this agreement is intended to imply that either the Sponsor or the Investigator(s) can prevent publication of the results.

## APPENDIX 1: KARNOFSKY PERFORMANCE STATUS SCALE DEFINITIONS RATING (%) CRITERIA

Able to carry on normal activity and to work; no special care needed.	100	Normal no complaints; no evidence of disease.
	90	Able to carry on normal activity; minor signs or symptoms of disease.
	80	Normal activity with effort; some signs or symptoms of disease.
Unable to work; able to live at home and care for most personal needs; varying amount of assistance needed.	70	Cares for self; unable to carry on normal activity or to do active work.
	60	Requires occasional assistance, but is able to care for most of his personal needs.
	50	Requires considerable assistance and frequent medical care.
Unable to care for self; requires equivalent of institutional or hospital care; disease may be progressing rapidly.	40	Disabled; requires special care and assistance.
	30	Severely disabled; hospital admission is indicated although death not imminent.
	20	Very sick; hospital admission necessary; active supportive treatment necessary.
	10	Moribund; fatal processes progressing rapidly.
	0	Dead

References:

de Haan R, Aaronson A, et al. Measuring quality of life in stroke. *Stroke*. 1993; 24:320- 327.

Oxford Textbook of Palliative Medicine, Oxford University Press. 1993;109.

4.3. Primary Efficacy Population.....	24
4.4. Evaluable Population	25
4.5. Induction Phase Dosing Compliant Population.....	25
4.6. Study Dosing Compliant Population	25
5. STATISTICAL METHODS	25

5.1. Subject Disposition, Demographic, and Baseline Characteristics	25
5.2. Efficacy Analysis	25
5.2.1. Primary Efficacy Endpoint.....	25
5.2.2. Primary Efficacy Analysis.....	26
5.2.3. Sensitivity Assessments for the Primary Efficacy Analysis.....	27
5.2.4. Additional Efficacy Endpoints	27
5.2.5. Additional Efficacy Analyses.....	27
5.2.6. Subgroup Analyses.....	27
5.3. Safety.....	27
5.3.1. Adverse Events.....	27
5.3.2. Study Drug Exposure and Concomitant Medications	28
5.3.3. Clinical Laboratory Assessments	28
5.3.4. Other Safety Analyses.....	28
6. PROTOCOL DEVIATIONS	29
7. CHANGES IN THE PLANNED ANALYSES	29
8. REVISION HISTORY	30
9. PROGRAMMING CONVENTIONS	31
10. PROPOSED TABLES, LISTINGS, AND FIGURES DSMB ANALYSES.....	33
11. PROPOSED TABLES, LISTINGS, AND FIGURES 6 MONTH ANALYSIS.....	35
12. PROPOSED TABLES, LISTINGS, AND FIGURES FINAL ANALYSIS.....	37

1 **INTRODUCTION**

This document describes the statistical methods and data presentations to be used in the summary and planned analysis of data from Protocol VB4-845-02-IIIA. Background information is provided for the overall study design and objectives. The reader is referred to the study protocol and case report forms (CRFs) for details of study conduct and data collection. Analyses of pharmacokinetic, EpCAM, and anti-Vicinium antibody data will be described in a separate Analysis Plan.

This analysis plan will serve as the final documentation for the planned statistical analyses for study VB4-845-02-IIIA and will supersede the protocol if there are any discrepancies.

1.1. **STUDY OVERVIEW**

This is an open-label, non-randomized, multicenter, multiple-dose, study of Vicinium in approximately 134 subjects with non-muscle invasive bladder cancer (NMIBC). Subjects will have histologically-confirmed non muscle-invasive carcinoma in situ (CIS) and/or papillary disease (high grade non-invasive papillary carcinoma (Ta) or any grade in which the tumor invades lamina propria (T1)) of the bladder who failed previous treatment (i.e., not those who are intolerant) with bacillus Calmette-Guérin (BCG).

All subjects must have received “adequate BCG treatment”, defined as at least 2 courses of full dose BCG i.e., at least one induction course of at least 5 doses given within 7 weeks, and a second course (maintenance or second induction) of at least 2 doses given within 6 weeks. A full dose BCG is one of the following

- TICE® BCG: one vial of TICE containing 1 to 8×10^8 colony-forming units (CFU) equivalent to approximately 50 mg (wet weight) or equivalent.
- ImmuCyst® BCG: one vial of ImmuCyst containing 81 mg (dry weight) equivalent to approximately $10.5 \pm 8.7 \times 10^8$ CFU or equivalent

The “5+2” doses must be completed within 1 year and given to treat the same disease episode with which the subject is enrolling. All subjects must have disease for which the investigator would not treat with additional BCG at this time.

Three cohorts of subjects will enroll:

- Cohort 1: Subjects with CIS with or without associated papillary disease whose disease is determined to be refractory or relapsed within 6 months of the last dose of adequate BCG treatment.
- Cohort 2: Subjects with CIS with or without associated papillary disease whose disease is determined to be refractory or relapsed more than 6 months but within 11 months of the last dose of adequate BCG treatment.
- Cohort 3: Subjects with high-grade Ta or any grade T1 papillary disease (without CIS) whose disease is determined to be refractory or relapsed within 6 months of the last dose of adequate BCG treatment.

For eligibility and cohort assignment 6 months is defined as 28 weeks i.e., 26 weeks (6 months) plus an additional 2 weeks for diagnostic work-up and 11 months is defined as 50 weeks i.e., 48 weeks (11 months) plus an additional 2 weeks for diagnostic work-up.

Of the 134 subjects, ≥ 77 will accrue to Cohort 1. Up to 57 additional subjects in total may accrue to Cohorts 2 and 3. This is an outpatient study. All treatments may be administered in the study clinic.

All diagnostic pathology (bladder tissue and urine cytologies and if performed, tissue from prostatic urethral biopsies) will be reviewed and graded by an independent pathologist and cytopathologist with experience in NMIBC diagnoses. The details of sample handling and logistics will be provided in a separate laboratory manual.

The sample used for determining subject eligibility for inclusion into the trial (post-BCG biopsy) must be reviewed and signed off by the pathologist prior to study enrollment and start of study treatment. All other samples will be read in a timely fashion and the results will be available to study investigators via the electronic CRF.

Each subject's study course consists of a Screening Period, a 12-week Induction Phase, a Maintenance Phase and a Post-Treatment Evaluation.

Following the 12-week Induction Phase, subjects will be evaluated for disease status as described in Protocol Section 14. Subjects without a treatment failure as specifically defined in Protocol Section 14.2 or other criteria necessitating discontinuation of study treatment (see Protocol Section 11.3) will begin the Maintenance Phase. Subjects will receive treatment for up to 2 years in total if they are tolerating treatment and do not meet the definition of protocol-defined treatment failure or other criteria for study discontinuation. Following the Post-Treatment Evaluation, additional subject data will be collected as needed for the evaluation of the Secondary Endpoints.

1.2. VISIT SCHEDULE AND ASSESSMENTS (SCREENING & INDUCTION)

Assessment	Screening and Baseline Weeks		Induction Phase Weeks 1-12					Post-Induction Phase
	Week -8 through -1	-1	1	2-5	6	7-11	12	
Week	-8 through -1	-1	1	2-5	6	7-11	12	As soon as possible after Week 12
Informed consent	X							
Inclusion/Exclusion criteria	X							
Cystoscopy	X ^{1,2}							X ²
Bladder biopsy/TURBT	X ¹							X ³
EpCAM determination, Biomarker evaluations ¹⁵	X ¹⁵							X ¹⁵
Urine Cytology			X ⁸					X ¹⁰
Demographics	X							
Medical and medication history (including previous anti-tumor therapy and surgical procedures)	X	X ⁶						
Physical examination		X	X ⁸	X ¹¹		X ¹¹	X ¹¹	
Weight and height		X ¹²		X ¹²		X ¹²	X ¹²	
Radiological imaging	X ⁴							
TriPLICATE ECG	X ⁵							X ¹¹
Vital signs	X		X ⁹	X ⁹	X ⁹	X ⁹	X ⁹	
Hematology		X	X ⁸	X ¹¹	X ¹¹	X ¹¹	X ¹¹	
Chemistry		X	X ⁸	X ¹¹	X ¹¹	X ¹¹	X ¹¹	
Urinalysis		X	X ⁸		X ¹¹		X ¹¹	
Anti-Vicinium antibody test	X							X
Plasma Vicinium Levels (PK) ¹⁴			X		X		X	
Serum or urine pregnancy test		X ⁷		X ⁷		X ⁷	X	
Concomitant medication			X ¹⁰	X ¹⁰	X ¹⁰	X ¹⁰	X ¹⁰	X
Adverse events (AEs / SAEs)			X ⁹	X ⁹	X ⁹	X ⁹	X ⁹	X
Drug administration (BIW) ¹³			X	X	X			
Drug administration (once/week)						X	X	

¹ Must have documented non-muscle invasive urothelial bladder cancer that is histologically confirmed by the independent central pathology reviewer prior to the first dose of study drug. All papillary disease must be completely resected. In subjects with T1 disease, a second (i.e., restaging) TURBT must be performed approximately 2 - 6 weeks after the first. A biopsy may be more than 8 weeks prior to the first dose of study drug as long as the last biopsy that confirms eligibility is within 8 weeks.

² White-light cystoscopy. Any subject who undergoes fluorescence cystoscopy for bladder biopsy/TURBT during the screening period must continue having this modality for all subsequent biopsies (however, white-light cystoscopy will suffice for all assessments if a biopsy is not required (Protocol Section 14).

³ Directed biopsies of all areas suspicious for disease. Random biopsies are required if cystoscopy is negative and urine cytology is positive or there are two suspicious cytology results (Protocol Section 14)

⁴ CT urogram or MRI urogram. If intravenous contrast is contraindicated, retrograde ureteropyelography, or CT or MRI without intravenous contrast may be performed. Required during Screening for all subjects with T1 disease. Required for all other subjects if not previously performed within 13 weeks before the start of dosing.

⁵ Single tracing only at Screening unless QTc is prolonged (Protocol Section 16.4); thereafter, triplicate ECGs are to be performed.

⁶ Update medication history.

⁷ Performed every 4 weeks (i.e., week 4, week 8, week 12, etc.) while on treatment in females of childbearing potential only.

⁸ Cytology sample pre-dose on Day 1. Note: Chemistry, hematology (CBC and differential), urinalysis and physical examination need to be performed pre-dose Day 1 only if not performed in the Baseline Period (≤ 7 days before the first dose of study medication).

⁹ Evaluation performed pre-dose and post-dose prior to leaving the clinic.

¹⁰ Evaluation performed pre-dose. Concomitant medications required post-dose only if additional medications (not including Vicinium) were administered during or after the start of the instillation.

¹¹ Weeks 2-5: Chemistry and hematology (CBC and differential) performed at any time once weekly (Protocol Section 10.3.2). Week 4: Targeted physical examination. Week 6: Urinalysis performed pre-dose at the second dose of the week; Hematology (CBC and differential) and chemistry (Protocol Section 10.3.3). Weeks 7-11: Chemistry and hematology (CBC and differential) performed at any time once weekly (Protocol Section 10.3.4). Week 8: Targeted physical examination. Week 12: Urinalysis performed pre-dose. Hematology (CBC and differential), chemistry (Protocol Section 10.3.5). Targeted physical examination and triplicate ECG performed post-dose prior to leaving the clinic.

¹² Height and weight at Baseline. Weight performed Week 4, Week 8 and Week 12.

¹³ Twice weekly (BIW) dosing with each dose separated by at least 48 hours (and no more than 2 doses within any calendar week (Sunday through Saturday)). As an example, while a Monday/Thursday or Tuesday/Friday would be optimal, a Monday/Wednesday or Tuesday/Thursday, or Wednesday/Friday dosing schedule could be used.

¹⁴ Levels are to be taken pre-dose of first instillation. Additional sampling is at the end of the dwell time as soon as possible (within 30 minutes) after the subject voids (or bladder is drained via catheter) following the first instillation and after the second of the twice-weekly instillations during Weeks 6 and 12.

¹⁵ For all bladder biopsy/TURBT samples positive for urothelial carcinoma (Protocol Section 16.7).

1.3. VISIT SCHEDULE AND ASSESSMENTS (MAINTENANCE PHASE)

Assessment	Maintenance Phase					Post-Treatment (30 – 37 days after last dose)
	Treatment Days	Every 2 Weeks	Every 4 Weeks	Every 13 Weeks	Between Weeks 23 and 27	
Cytology				X ^{1,10}		X ^{1,6}
Cystoscopy				X ^{1,2,10}		X ^{2,3,6}
Biopsy/TURBT				X ^{1,3,10,13}		X ^{2,3,6,13}
Physical examination			X ⁷			X ⁷
TriPLICATE ECG						X
Vital signs	X ⁴					X
Weight			X			X
Anti-Vicinium antibody test					X	X
Chemistry		X ¹²				X
Hematology and urinalysis			X ⁹			X
Urine or serum pregnancy test			X ⁵			X
Concomitant medication	X ⁴					X ⁸
Adverse events (AEs / SAEs)	X ⁴					X
Drug administration (once every other week)	X					
Contact to assess for progression and survival				X ¹¹		

¹ Window of 1 week before to 2 weeks after to start evaluation

² White-light cystoscopy. Any subject who underwent fluorescence cystoscopy for bladder biopsy/TURBT during the screening period must continue having this modality for all subsequent biopsies (however, white-light cystoscopy will suffice for all assessments if a biopsy is not required (Protocol Section 14).

³ Directed biopsies of all areas suspicious for disease. Random biopsies are required if cystoscopy is negative and urine cytology is positive or there are two suspicious cytology results (Protocol Section 14)

⁴ Evaluation performed pre-dose and post-dose prior to leaving the clinic. Concomitant medications required post-dose only if additional medications (not including Vicinium) were administered during or after the start of the instillation

⁵ Performed every 4 weeks during study participation in females of childbearing potential only.

⁶ Evaluations performed if the subject has not discontinued treatment due to documented disease recurrence, progression and if they have not been performed within the past 8 weeks.

⁷ Targeted physical examination.

⁸ Additional follow-up will occur for subjects with ongoing clinically significant AEs (e.g., those leading to study drug discontinuation) or SAEs assessed as related to study drug.

⁹ Urinalysis performed pre-dose if on a treatment day.

¹⁰ Weeks 26, 39, 52, 65, 78, 91, 104

¹¹ Starting after subject discontinues study drug. Progression will be assessed if the subject did not have disease progression as the reason for discontinuation of study drug and has not had a cystectomy.

¹² Protocol Section 10.5.2.

¹³ EpCAM and biomarker evaluation on all bladder biopsy/TURBT samples positive for urothelial carcinoma (Protocol Section 16.7).

1.4. LIST OF ABBREVIATIONS

Abbreviation	
AE	adverse event
BCG	bacillus Calmette-Guérin
BIW	twice weekly
CFU	colony forming units
CIS	carcinoma in situ
CRF	case report form
CT	computerized tomography
CTCAE	Common Terminology Criteria for Adverse Events
DSMB	data safety monitoring board
ECG	electrocardiogram
FDA	Food and Drug Administration
EFS	event-free survival
EpCAM	epithelial cell adhesion molecule
MedDRA	Medical Dictionary for Regulatory Activities
mITT	modified intent-to-treat
MRI	magnetic resonance imaging
NCI	National Cancer Institute
NMIBC	non-muscle invasive bladder cancer
OS	overall survival
PFS	progression-free survival
PK	pharmacokinetics
QTc	corrected QT interval
QTcB	corrected QT interval - Bazett's correction
QTcF	corrected QT interval - Fridericia correction
SAE	serious adverse event
SD	standard deviation
SOC	system organ class
Ta	non-invasive papillary carcinoma
T1	tumor invades lamina propria
T2	tumor invades muscularis propria
TEAE	treatment-emergent adverse event
TPP	time to progression
TURBT	transurethral resection of bladder tumor(s)

2. **OBJECTIVES**

To assess the efficacy and tolerability of Vicinium when administered as a monotherapy intravesical instillation in subjects with non-muscle invasive bladder cancer - CIS, high-grade Ta or any grade T1 papillary disease or CIS plus papillary disease who failed previous treatment (i.e., not those who are intolerant) with BCG.

Primary endpoints:

Complete response rate at 3 months in subjects with CIS (with or without papillary disease) whose disease is refractory or relapsed in 6 months or less or relapsed from 6 months to 11 months following adequate BCG treatment.

Duration of response (DoR) will be estimated (Kaplan-Meier Estimate) for those subjects with CIS (with or without papillary disease) who experience a complete response.

Secondary endpoints:

- Complete response rate in subjects at 6, 9, 12, 15, 18, 21, and 24 months in subjects with CIS
- Event free survival (EFS) in all subjects
- Cystectomy-Free Days in all subjects
- Time to disease recurrence in papillary subjects
- Progression-free survival (PFS) in all subjects
- Overall survival (OS) in all subjects
- Safety and tolerability of Vicinium therapy in all subjects

Exploratory:

To evaluate biomarkers that may be associated with response or disease progression or treatment failure, which may include, for example, EpCAM status, tumor subtype morphology, furin levels in tumor cell endosomes, presence of a glycosaminoglycan coat, and presence of receptors that could impede a host anti-tumor immune response such as PD-L1.

3. **GENERAL STATISTICAL CONSIDERATIONS**

3.1. **SAMPLE SIZE AND POWER**

Assuming the true complete response rate at 12 months is 30%, sample sizes associated with various widths of a two-sided, exact (Clopper-Pearson) 95% confidence intervals are provided in the table below:

Sample Size (N)	Target Distance from P to Lower Limit	Proportion (P)	Lower Limit
121	0.080	0.300	0.220
95	0.090	0.300	0.210
76	0.100	0.300	0.200

Under the provided assumptions, a sample size of ≥ 77 evaluable subjects with early relapsed/refractory CIS with or without papillary disease is sufficient to estimate complete response rate with an exact 95% confidence interval that excludes 0.2 (PASS 2008).

The secondary endpoint of event-free survival (EFS) will be used to assess the treatment effect in all subjects, i.e., those with CIS (with or without papillary disease) and those with papillary-only disease. An estimate of EFS at the 18 month time-point will be calculated. The total sample size of 134 subjects will provide at least 80% power to test the null hypothesis that the event-free survival rate at 18 months is 20% versus the alternative hypothesis that the event-free survival rate at 18 months is $\geq 30\%$. This calculation is based on the assumptions of a nonparametric distribution for event-free survival and the length of follow-up is 24 months.

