## 17 STATISTICS

### 17.1 General Principles of Statistical Analysis

The type I (alpha error) for all hypothesis testing will be set at 0.05, and all statistical tests will be two-sided. All confidence intervals will be two-sided 95% confidence intervals. Data will be summarized by reporting the frequency and percentage of subjects in each category for categorical and ordinal measures, and means, standard deviations (SD), medians, minimum and maximum for continuous measures.

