5. STATISTICAL METHODS

Descriptive statistical methods will be used to summarize the data from this study, with hypothesis testing performed for the primary and other selected efficacy endpoints. Unless stated otherwise, the term “descriptive statistics” refers to number of subjects (n), mean, median, standard deviation (SD), minimum, and maximum for continuous data and frequencies and percentages for categorical data.

All data collected during the study will be included in data listings. Unless otherwise noted, the data will be sorted first by subject number and then by phase (induction, maintenance), cycle/visit, and date.

Unless otherwise specified, all statistical testing will be two-sided, and will be performed using a significance (alpha) level of 0.05.

The statistical analyses will be conducted with the SAS® software package version 9.2 or higher. All analyses will be subject to formal verification procedures. Specifically, results will be verified utilizing independent programming prior to issuance of the draft statistical report. All documents will be verified by the lead statistician to ensure accuracy and consistency of analyses.

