5.2.5. Additional Efficacy Analyses

The following analyses will be conducted in the mITT population, the evaluable population, the induction phase dosing compliant population, and the study dosing compliant population.

EFS will be estimated using the method of Kaplan-Meier. Subjects without evidence of a treatment failure who are diagnosed with upper or lower urinary tract urothelial carcinoma by histology, cytology or radiographic evidence will be censored at the date of diagnosis. Subjects without evidence of a treatment failure who undergo cystectomy will be censored at the date of cystectomy. All other subjects will be censored at the time of the last assessment. The ninety-five percent (95%) confidence interval around the EFS rate at 18 months will be presented.

Time to disease recurrence will be estimated separately for each cohort using the method of Kaplan-Meier. For subjects in Cohort 3, time to disease recurrence is defined as the number of days from first dose of study treatment to the first occurrence of treatment failure. Subjects who do not experience treatment failure will be censored at the last assessment.

Cystectomy-free days, time to progression, progression-free survival, and overall survival will be estimated based on the method of Kaplan-Meier.

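### The claim of at least 80% power for 18-month EFS with 134 subjects is not supported at the two-sided 5% level; about 75% is, before any censoring

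*SAP*

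**What the plan says.** SAP 3.1 and Protocol 17.8 carry the same statement, and the synopsis repeats it in substance: "The total sample size of 134 subjects will provide at least 80% power to test the null hypothesis that the event-free survival rate" (null 20%, alternative 30% or more, both for month 18). The stated basis is the "assumptions of a nonparametric distribution for event-free survival and the length of follow-up is 24 months". No test, interval type, software or dropout allowance is named for this calculation.

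On the error level, Protocol 17.1 says: "The type I (alpha error) for all hypothesis testing will be set at 0.05, and all statistical tests will be two-sided". SAP 5 agrees, unless otherwise specified: "all statistical testing will be two-sided, and will be performed using a significance (alpha) level of 0.05". The power statement specifies nothing different.

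On the analysis, SAP 5.2.5 plans a Kaplan-Meier estimate and says: "The ninety-five percent (95%) confidence interval around the EFS rate at 18 months will be presented". Protocol 17.5 plans the same. Neither gives the transformation used for the interval or a success rule for EFS.

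**The concern.** Sample size, null rate, alternative rate and error level are all stated, so the power can be checked. Methods that keep the upper-tail error within 2.5% fall short of 80%, and the planned analysis includes censoring that the calculation does not allow for.

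This is the only power figure in the documents and the only justification attached to the total of 134; the statement about at least 77 subjects in Cohort 1 concerns interval precision for complete response. A reader of an EFS interval that fails to exclude 20% would think the chance of that outcome, if the true rate were 30%, was at most 20%. Without censoring it is about 24.5% (1 − 0.755), and more with censoring.

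**Working it through.** **Inputs.** n = 134, p0 = 0.20, p1 = 0.30 (SAP 3.1, Protocol 17.8). Two-sided 5%, so z = 1.96 and 0.025 in the upper tail (Protocol 17.1, SAP 5). With 24 months of follow-up for all, there is no administrative censoring before month 18. The documents give no other censoring rate.

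**1. Reproducing the stated figure.** The usual normal approximation, with the null variance in the critical value and the alternative variance for power, is

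Φ[((p1 − p0)√n − z√(p0q0)) / √(p1q1)] = Φ[(0.1 × 11.576 − 1.96 × 0.4) / 0.4583] = Φ(0.815) = **79.3%**.

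Sample size for 80%: [(1.96 × 0.4 + 0.8416 × 0.4583) / 0.1]² = 136.8, so 137. This comes close to the plan's figure but stays just below it. Other two-sided approximations give 76.6% (arcsine), 76.5% (continuity-corrected), 71.4% (alternative variance throughout) and 82.5% (null variance throughout, which uses the wrong variance under the alternative).

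**2. Exact rejection rules, no censoring.** The Kaplan-Meier estimate is then a simple proportion. Lower 95% limits:

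| Interval | 36/134 (26.9%) | 37/134 (27.6%) |
|---|---|---|
| Linear | 0.194 | 0.2004 |
| Clopper-Pearson | 0.196 | 0.202 |
| Log-log | 0.197 | 0.203 |
| Logit | 0.2005 | 0.207 |
| Wilson (score) | 0.2008 | 0.207 |
| Log | 0.203 | 0.210 |

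The first three exclude 0.20 only from 37 event-free subjects. The last three exclude it from 36. From the binomial distribution:

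- Reject at ≥37: P(X ≥ 37 | 0.20) = 0.021 and power P(X ≥ 37 | 0.30) = **75.5%**.
- Reject at ≥36: P(X ≥ 36 | 0.20) = 0.033 and power P(X ≥ 36 | 0.30) = **81.1%**. The two-sided score test also rejects at ≤17, with probability 0.018, so its total size is 0.033 + 0.018 = 0.052.

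Exact power first reaches 80% at N = 144 and stays there from N = 155 (checked over the next 40 sample sizes).

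**3. With censoring.** SAP 3.3.7 censors EFS for cystectomy, upper or lower tract disease, new anti-cancer therapy, a second cancer, and death after treatment discontinuation. It also says that disease assessments are not recorded after treatment discontinuation. The rates below are assumptions. Event and censoring times are taken as exponential, with 20,000 simulated trials per setting (simulation error about 0.3 points; a range shows separate runs):

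| Assumed loss before month 18 | Linear | Log-log | Logit | Log |
|---|---|---|---|---|
| 0% | 75% | 75% | 81% | 81% |
| 10% | 70% | 73% | 77% | 79% |
| 20% | 66–67% | 70% | 74% | 76–77% |

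At an assumed 5% loss, the most favourable type (log) is already at 79.6%.

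**The case against.** The strongest reply is that the documents name no exact test for EFS. Clopper-Pearson is specified for complete response only, and the Kaplan-Meier interval type is left open. A two-sided score test, a Wilson interval, or a log- or logit-scale interval is a recognised nominal 5% method, and each gives 81.1% without censoring. The usual approximation gives 79.3%, and 134 is only three short of 137. The loss rates appear nowhere in the documents, and EFS is secondary with no stated success rule.

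Much of this stands. A reader might infer that no standard two-sided method reaches 80%, or that 81% needs a one-sided 5% test. Neither is correct. A one-sided exact test does give 81.1%, but so do the two-sided methods above, and the documents do not show that a one-sided level was used. Nor can about 75% be called the power of the planned interval without qualification, because its type is unspecified.

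The power statement is still not supported. The methods that reach 81.1% do so by letting the upper-tail error rise to 0.033, and only with almost complete follow-up. The usual approximation also falls short of a claim worded as a minimum.

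**Conclusion.** The stated power is overstated. At two-sided 5% with no censoring it is 75.5% for an exact test or a linear or log-log Kaplan-Meier interval, and 79.3% by the usual approximation. The 81.1% figure requires a method whose upper-tail error exceeds 2.5%. Under an assumed 10% loss, all four Kaplan-Meier interval types fall below 80%.

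The uncensored figures follow from the documents' inputs, taking rejection to mean that the lower limit exceeds 20%; the documents do not state this rule for EFS. The direction of the censoring effect follows from the SAP's rules, but its size rests on assumed rates and exponential times.

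A reader might infer that the whole trial is underpowered. The documents do not support that: the primary endpoint is complete response, justified separately by interval width. The point should be corrected, but it does not bear on the primary conclusion.

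**What to change.** In SAP 3.1, Protocol 17.8 and the synopsis:

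- Name the test or interval type for 18-month EFS, for example a log-log Kaplan-Meier 95% interval with its lower limit above 20%, and use the same in SAP 5.2.5.
- Restate the power as about 75% at two-sided 5% with 134 subjects, 20% against 30%, and no censoring before month 18.
- Add a lower figure under an explicitly labelled censoring assumption. For the log-log interval this is about 73% at 10% loss and 70% at 20%.

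This is a change of wording, with no effect on enrolment or conduct. The cost is a less favourable stated power for a secondary endpoint.
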